
STATISTICS Primary Analysis Plan
	
Analysis of insomnia treatment will be conducted only for patients matching inclusion and exclusion criteria who will complete at least one treatment course (BBT-I or medication) and fill in questionnaires prior and after the treatment. Continuous variables will be presented in means and standard deviation (M±SD). Categorical and rank variables will be presented as percentages.
 
Statistical significance of differences between group for continuous variables will be evaluated with Student’s t-test after confirmation of normal variable distribution by Kolmogorov-Smirnov test.
 
For continuous variables with distribution other than normal Mann-Whitney U-test will be used. For comparison of the proportions Pearson chi-squared test will be performed.
 
Criterion of response to the treatment is defined as the reduction of ISI score reduction of >7 points from baseline. Remission criterion is defined as final ISI score of 7 points or less. Nonresponse criterion is defined as ISI score decrease of ≤7 points from baseline. Based on these dichotomic values participants will be divided into two groups: responders and nonresponders for each method of treatment.
 
Comparison of responders and nonresponders baseline quantitative characteristics will be performed using Student’s t-test (for normal data distribution) or Mann-Whitney U-test (for abnormal data distribution). Statistical significance will be set at a p-value less 0,05.

Rationale for Number of Subjects
	
Study design allows to compare two therapeutic approaches with a relatively small sample size and to determine the predictors of effectiveness for each treatment. Thus 40 patients get 2 therapeutic approaches. This is the representative sample size enough to produce normal variable distribution for further parameter statistical analysis.

PURPOSE OF THE INVESTIGATION

Name of investigational method

Brief behavioral therapy program
Imovan (zopiclone)

Intended use of the investigational method

2-week Brief behavioral therapy will be performed in two 1 hour session for treatment of chronic insomnia (CI)

Imovan (zopiclone) in a dose of 7,5 mg has to be taken 30 minutes before bedtime for two weeks

Overview of Clinical Studies

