To test the effectiveness of short BBT-I program for chronic insomnia in comparison with zopiclone in Russian population.

Secondary Objectives

Identification of anthropometric, psychological and polysomnographic predictors of effectiveness of each method.

STUDY DESIGN

Study Overview

Prospective randomized crossover study. In accordance with this design every patient will receive two different treatment courses in random sequence: zopiclone or structured educational program (BBT-I) delivered in two sessions. Patients of the zopiclone-first group will receive the medication therapy for the first two weeks followed by educational program. Patients of the BBT-I-first group will receive two-week educational program followed by medication therapy.

Each treatment course will be separated by 2-weeks washout period that will provide the opportunity to evaluate the sustainability of treatment effect.

The total duration of the study will be 8 weeks with 6 visits including 1 night polysomnography (PSG), 2 face-to-face structured educational program sessions and 5 diagnostic interviews. Total duration of the study will be 2 years.

Criteria for evaluation

Primary Efficacy Endpoint

Proposed primary efficacy endpoint is change of insomnia severity index (ISI) after treatment. Criterion of response to the treatment will be defined as the reduction of ISI score reduction of >7 points from baseline. This criterion is indicative of moderate improvement and validated as clinically significant (Morin, Belleville & Belanger, 2011). Remission criterion will be defined as final

ISI score of 7 points or less. Nonresponse criterion will be defined as ISI score decrease of ≤ 7 points from baseline.

Secondary Efficacy Endpoints

1. Insomnia severity index self reported insomnia symptoms severity . Each item is scored 0 (no problem) - 4 (very big problem) with total between 0-28 (absence of insomnia (0-7); sub-threshold insomnia (8-14); moderate insomnia (15-21); and severe insomnia (22-28).
2. Beck Depression Inventory. 21-item questionnaire assessing (on 4-point Likert scales) the intensity of depressive symptoms in the past week
3. State-trait anxiety inventory. 2-part questionnaire assessing state (situational) and trait anxiety. Both situational and trait parts comprise 20 items rated on a 4-point Likert scale.
4. Dysfunctional beliefs about sleep scale. questionnaire assessing sleep related cognitions in 16 item rated on a 10-point Likert scale.

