Subjects withdrawn from the study treatment will be replaced. Subjects withdrawn from the study after Visit 5 but prior to Visit 6 won't be replaced.

Protocol Violations

Protocol violations for this study include, but are not limited to, the following:

- Failure to meet inclusion/exclusion criteria

- Use of a prohibited concomitant medication
- Non-compliance with study drug regimen, and questionnaires completion

Failure to comply with Good Clinical Practice (GCP) guidelines will also result in a protocol violation. If a protocol violation occurs, a Protocol Violation Form detailing the violation will be generated.

DATA SAFETY MONITORING

There will be no data monitoring committee

STATISTICAL METHODS AND CONSIDERATIONS

A Statistical Analysis Plan (SAP) is written describing all analyses that will be performed.

Data Sets Analyzed

All subjects matching inclusion and exclusion criteria who will complete at least one treatment course (BBT-I or medication) and fill in questionnaires prior and after the treatment will be included in the safety analysis.

Demographic and Baseline Characteristics

The following demographic variables at screening will be summarized by dose level: gender, age, height and weight. Continuous variables will be presented in means and standard deviation ($M \pm SD$).

Analysis of Primary Endpoint

Statistical significance of differences between ISI level before and after treatment for both treatment methods will be evaluated with Student's t-test after confirmation of normal variable distribution by Kolmogorov-Smirnov test. For continuous variables with distribution other than normal Mann-Whitney U-test will be used. For comparison of the proportions Pearson chi-squared test will be performed.

Criterion of response to the treatment is defined as the reduction of ISI score reduction of >7 points from baseline. This criterion is indicative of moderate improvement and validated as clinically significant (Morin, Belleville & Belanger, 2011). As well the criterion corresponds to approximately 1 standard deviation of the pretreatment values (Cohen effect size of approximately 1.0). Remission criterion is defined as final ISI score of 7 points or less. Nonresponse criterion is defined as ISI score decrease of ≤ 7 points from baseline.

Analysis of Secondary Endpoints

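### The only defined ISI tests compare before with after for each method; the BBT-I versus zopiclone contrast and the second-course baseline are left undefined

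*Combined protocol and SAP*

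**What the plan says.** All references are to the combined protocol and SAP.

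- **Primary Objective:** "To test the effectiveness of short BBT-I program for chronic insomnia in comparison with zopiclone in Russian population".
- **Primary Efficacy Endpoint:** "Proposed primary efficacy endpoint is change of insomnia severity index (ISI) after treatment". Response is a fall of more than 7 points from baseline; remission is a final score of 7 or less.
- **Analysis of Primary Endpoint:** "differences between ISI level before and after treatment for both treatment methods will be evaluated with" Student's t-test if a Kolmogorov-Smirnov check supports normality. It continues: "For continuous variables with distribution other than normal Mann-Whitney U-test will be used. For comparison of the proportions Pearson chi-squared test will be performed".
- **Synopsis, Primary Analysis Plan:** "Statistical significance of differences between group for continuous variables will be evaluated with" the same t-test, with the same fallback and the same chi-squared test. Patients are analysed if they "complete at least one treatment course (BBT-I or medication) and fill in questionnaires prior and after the treatment".
- **Study Overview:** each patient receives both courses in random order, separated by a "2-weeks washout period that will provide the opportunity to evaluate the sustainability of treatment effect".
- **Sample Size and Randomization:** 40 subjects; the crossover is the reason given for a small sample. No method of comparing the two treatments is named there.

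ISI is collected at the baseline examination and the next four visits (Questionnaire section). Visit 2 ends the first course, visit 3 starts the second and visit 4 ends it. No section names a paired test, McNemar's test, a mixed model, or a period or sequence term.

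**The concern.** A significant fall under each method says nothing about the difference between them. Any fall counts, including regression to the mean and natural course, so both tests can be significant when the methods are equal and also when they differ. With small falls, one test can be significant and the other not by chance, which invites a false claim that one method is better.

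If the undefined between-group or chi-squared test is meant to fill the gap, its result depends on choices the plan does not make: which groups, which visit, and which starting value for the second course. The study is open-label and the investigator is responsible for data processing, so these choices could be made after the data are seen.

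**Working it through.** **Inputs.** N = 40 (Sample Size and Randomization), taken as 20 per sequence with both courses completed. The score SD is about 7, because the more-than-7-point criterion is said to match the pretreatment SD: "As well the criterion corresponds to approximately 1 standard deviation of the pretreatment values". Alpha is 0.05, taken as two-sided. The documents give no SD of change and no correlation, so those are assumed and varied. The plan gives no derivation of N = 40, so there is no stated figure to reproduce. Results other than the direct formulas are from simulation with normal scores, 20,000 to 100,000 trials per setting.

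**1. Before/after tests as written, run as paired t-tests.** SD of change = 7 × √(2(1 − r)), which is 8.28, 7.00 and 5.42 at before/after correlation r = 0.3, 0.5 and 0.7. The correlation between the two changes is set at 0 to 0.5.

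| True falls | Both significant | Exactly one significant |
|---|---|---|
| 4 and 4 | 72–99% | – |
| 4 and 7 | 85–99.5% | – |
| 3 and 3 | – | 11–48% |
| 7 and 7 | – | about 0.1% or less |

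The first two rows barely distinguish equal methods from methods 3 points apart.

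**2. Between-group read as the randomised sequences, compared at visit 2.** The groups are independent and the test is valid. SE = 7 × √(2/20) = 2.21, and 3/2.21 = 1.36, giving power of about 26% for a 3-point difference. If change from visit 1 is compared instead, power is 20–55% over correlations 0.3 to 0.8. Only the first course is used.

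**3. Between-group read as the two methods pooled over courses.** Each two-course patient is then in both groups, and an independent-samples t-test ignores this. Visit correlations are equal (0.3–0.7) or decaying (0.5–0.8 per visit), with no carry-over.

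| Second-course baseline | Type I error, unpaired t | Power at 3 points, unpaired | Power at 3 points, period-difference test |
|---|---|---|---|
| Visit 1 | 0.6–0.9% | 31–75% | 58–93% |
| Own start (visit 3) | 4.9–6.4% | 36–84% | 35–81% |

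Check of the first row: with equal correlations, two changes from a common baseline correlate at 0.5. The true SE is therefore √0.5 of the one used, and 2 × (1 − Φ(1.96/√0.5)) = 0.6%.

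Chi-squared on response behaves similarly. With a visit 1 baseline, type I error is 1.8–2.3% against 4.4–5.0% for McNemar, and power is 22–49% against 32–63% (mean falls 7 and 10). With own start, type I error is 5.5–6.9% against 5.1–5.6%, and pairing gains no power.

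**4. Mann-Whitney on a patient's own before and after values.** The test assumes independence. Positive correlation r shrinks the true SE by about √(1 − r), so type I error is about 2 × (1 − Φ(1.96/√(1 − r))): 1.9% at r = 0.3 and under 0.1% at r = 0.7, instead of 5%.

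**5. Which baseline for the primary contrast.** With a common visit 1 baseline, the contrast is half the sequence difference in (visit 2 − visit 4). It equals the true difference minus half of (BBT-I carry-over − zopiclone carry-over). If BBT-I leaves ISI 2 points lower at visits 3 and 4, the bias is 1 point against BBT-I. Type I error is then 11–21% with equal methods, and power for a true 3-point BBT-I advantage is 30–63%. With own starts the same constant carry-over cancels within the second course: type I error stays at about 5% and power at 35–81%.

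**The case against.** The strongest objection is that the synopsis does contain a between-group test, and the protocol repeatedly uses group for the randomised sequences, including under Method of Assigning Subjects to Treatment Groups. On that reading the named tests are applied to independent groups and a valid randomised comparison exists. This stands as far as it goes. But the statistical text does not say so: the only groups it defines are responders and nonresponders within each method, for the predictor objective. That comparison would also discard the second course, which is the reason given for the small sample.

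A reader might infer that the named tests always lose power or distort error rates because pairing is ignored. The documents do not support that. The penalty on the between-method comparison arises only with a visit 1 baseline; with own starts the unpaired test is near nominal and pairing gains nothing. The references to questionnaires before and after a course fit own starts, whereas baseline in the response criterion may mean visit 1.

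A reader might also infer that the missing period term biases the comparison. With 20 per sequence a plain paired test is unbiased; at 24/16 with an assumed 2-point period effect the bias is 2 × 8/40 = 0.4 points. Nor are discordant before/after results to be expected generally: at 7-point falls, about the response threshold, they almost never occur.

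Student's t-test could be run as a paired test, but this is not said, and its stated fallback is for independent samples. Finally, the statistical section says a SAP is written. No further SAP text was supplied, so the point is limited to the combined document.

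**Conclusion.** The point holds and should be fixed before analysis. In the supplied document, the comparative primary objective has no defined ISI test, and the before/after tests that are defined cannot answer it. That conclusion needs no simulation.

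Its practical size depends on an SD of 7 inferred from one approximate sentence, on assumed correlations, on 20 patients per sequence and, except in step 5, on no carry-over. Under those assumptions, power for a 3-point difference runs from about 20% to 84% across the readings the text allows. Type I error for a between-method t-test runs from under 1% to about 6.5%. The choice of second-course baseline is part of the defect: it decides whether pairing helps and how far carry-over biases the result.

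**What to change.** In the synopsis and the Analysis of Primary Endpoint, prespecify one primary analysis: the BBT-I minus zopiclone difference in ISI change, with a 95% confidence interval. Compute each patient's first-course change minus second-course change and compare it between sequences with a two-sample t-test; the estimate is half the difference in sequence means. If normality fails, use the rank-sum test on the same differences.

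State the second-course baseline. The Overview of Clinical Studies describes lasting effects of behavioural treatment, and the washout is meant to observe persistence. Each course's own start (visit 1, visit 3) is therefore the safer primary choice. It removes carry-over that stays constant from visit 3 to visit 4, but not carry-over that fades between them. Report the visit 1 contrast and the first-period visit 2 comparison as sensitivity analyses.

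For response and remission between methods, use Mainland-Gart, or McNemar without period adjustment. Keep before/after changes as description; if tested, use a paired t-test or Wilcoxon signed-rank.

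**Cost.** Wording only, with no new patients or visits. ISI is already planned at all five main visits, though the questionnaire row in Appendix 1 omits it and should list it. Without carry-over, own starts give power of 35–81% against 58–93% for visit 1 at 3 points. One-course patients, whom the synopsis keeps, drop out of the period-difference test; a mixed model with treatment, period and sequence as fixed effects and patient as random can retain them as a sensitivity analysis.

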All concomitant medication and concurrent therapies will be documented at baseline examination and at visit days. Dose, route, unit frequency of administration, and indication for administration and dates of medication will be captured.

Demographics

Demographic information (date of birth, gender) will be recorded at baseline examination.

Medical History

Relevant medical history, including history of current disease, other insomnia history, and information regarding underlying diseases will be recorded at baseline examination.

Physical Examination

A complete physical and neurological examination will be performed by the investigator who is a neurologist at baseline examination.

Vital Signs

Body temperature, blood pressure, pulse will be measured after resting for 5 minutes at baseline examination.

Polysomnography

1-night in-lab PSG (without adaptation night) will be performed at baseline examination. Standard polysomnography montage includes 6 monopolar electroencephalography (EEG) channels Fp₁A₂, Fp₂A₁, C₃A₂, C₄A₁, O₁A₂, O₂A₁; 1 submental electromyogram (EMG) channel; 2 electrooculogram (EOG) channels; 2 EMG channels of the right and left tibialis anterior muscles; 1 electrocardiogram channel; oronasal airflow pressure; thoracic and abdominal efforts; respiratory sound; oxygen saturation; body position with videomonitoring

Questionnaire

Subjects will be asked to fill in self-report questionnaires: Beck Depression Inventory (BDI), State-trait anxiety inventory (STAI), Toronto Alexithymia Scale – short version TAS-20, Big Five Questionnaire (BFQ-2R), Pittsburg Sleep Quality Index (PSQI), Insomnia Severity Index (ISI), Dysfunctional beliefs about sleep scale (DBAS), Sleep hygiene index (SHI) at baseline examination.

During the next 4 visits participants will repeatedly undergo diagnostic tests including BDI, STAI, PSQI, ISI, DBAS, SHI.

Adverse Events

Information regarding occurrence of adverse events will be captured throughout the study. Duration (start and stop dates and times), severity, outcome, treatment and relation to study drug will be recorded on the case report form (CRF).

Clinical Laboratory Measurements

β -adrenoreactivity test

Peripheral blood sample will be collected in a sterile tube and tested in lab for erythrocyte membranes β -adrenoreactivity by a method based on detection of adrenoreceptor sensitivity to-endogenous catecholamines

EVALUATIONS BY VISIT

Visit 1 (Day 1/Week 1/ Month 1)

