Statistical significance of differences between BDI, STAI, PSQI, DBAS, SHI, β -adrenoreactivity level, sleep diary data before and after treatment for both treatment methods will be evaluated with Student's t-test after confirmation of normal variable distribution by Kolmogorov-Smirnov test. For continuous variables with distribution

other than normal Mann-Whitney U-test will be used. For comparison of the proportions Pearson chi-squared test will be performed.

Based on the response criterion participants will be divided into two groups: responders and nonresponders for each method of treatment. Comparison of responders and nonresponders baseline quantitative characteristics (polysomnographic, antropometric, psychometric) will be performed using Student's t-test (for normal data distribution) or Mann-Whitney U-test (for abnormal data distribution). Statistical significance will be set at a p-value less 0,05.

Safety and tolerability data will be summarized by treatment group. Adverse events will be tabulated by treatment group and include the number of patients for whom the event occurred, the rate of occurrence, and the severity and relationship to study drug.

Interim Analysis

Interim statistical analysis will be performed after 20 patients complete the study protocol.

Sample Size and Randomization

The number of subjects planned to be enrolled is 40. This is a representative sample for study of treatment effects. The crossover design of the study will allow us to compare two therapeutic approaches with a relatively small sample size and to determine the predictors of effectiveness for each treatment.

DATA COLLECTION, RETENTION AND MONITORING

Data Collection Instruments

The Investigator will prepare and maintain adequate and accurate source documents designed to record all observations and other pertinent data for each study subject. The information corresponding to each visit will be entered to the study database and to paper CRF.

The Investigator is responsible for all information collected on subjects enrolled in this study. All data collected during the course of this study will be reviewed and verified for completeness and accuracy by the Investigator.

Data Management Procedures

The data will be entered into a validated database. The Investigator is responsible for data processing, in accordance with procedural documentation.

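### The fallback test for before/after scores in the same patients is the independent-samples Mann-Whitney test, and no paired test is named anywhere in the plan

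*Combined protocol and SAP*

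**What the plan says.** Under Statistical Methods and Considerations, Analysis of Primary Endpoint, the rule for ISI is that "differences between ISI level before and after treatment for both treatment methods will be evaluated with" a t-test of Student's type, not labelled paired or unpaired. The condition set for using it is "after confirmation of normal variable distribution by Kolmogorov-Smirnov test". The next sentences read "For continuous variables with distribution other than normal Mann-Whitney U-test will be used" and "For comparison of the proportions Pearson chi-squared test will be performed". Analysis of Secondary Endpoints repeats the rule for BDI, STAI, PSQI, DBAS, SHI, β-adrenoreactivity and sleep diary data. The synopsis lists the same tests but describes them as comparisons between groups.

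The data are repeated measurements on the same people:

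- Study Overview: "every patient will receive two different treatment courses in random sequence".
- Questionnaire: "During the next 4 visits participants will repeatedly undergo diagnostic tests including BDI, STAI, PSQI, ISI, DBAS, SHI".
- Data Sets Analyzed: patients must "fill in questionnaires prior and after the treatment".

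The level is given by "Statistical significance will be set at a p-value less 0,05", without sidedness. The documents do not name a paired t-test, a signed-rank test, McNemar's test, a crossover model or a mixed model. They also do not say which variable is tested for normality (raw scores or differences), at what level, or whether the Kolmogorov-Smirnov (K-S) test is corrected for an estimated mean and SD.

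**The concern.** A before/after comparison in one set of patients is a paired problem. Mann-Whitney treats the two columns of scores as if they came from different people and ignores the within-patient correlation. If that correlation is positive, the test overstates the standard error, so its p-values are too large and real changes may be missed. A t-test run unpaired has the same defect.

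The sample-size sections justify 40 patients by the economy of the crossover design, and an unpaired test gives that economy away. How often it happens depends on a pretest that the plan leaves undefined.

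**Working it through.** **Inputs.** From the documents: n = 40; level 0.05 (two-sided assumed); SD of ISI about 7, because Analysis of Primary Endpoint equates the 7-point response criterion with about one pretreatment SD. Assumed: within-patient correlation ρ = 0.3, 0.5, 0.7, and the score shapes. The plan states no power or planning effect, so it has no figure of its own to reproduce.

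**1. True size of an unpaired test on paired data.** The mean difference has variance 2·SD²(1−ρ)/n, but the unpaired test uses 2·SD²/n. True size is therefore 2[1 − Φ(1.96/√(1−ρ))]:

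- ρ = 0.3: 1.96/0.837 = 2.34, size 0.019
- ρ = 0.5: 1.96/0.707 = 2.77, size 0.0056
- ρ = 0.7: 1.96/0.548 = 3.58, size 0.0003

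Simulated Mann-Whitney sizes agree: about 2-3%, 0.5-1% and 0.1-0.2%. Only a negative correlation would reverse the direction (0.086 at ρ = −0.3).

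**2. Power of an unpaired t-test, normal scores.** Take changes d = 3.76, 3.18 and 2.46 points, at which the paired t-test has 80% power for the three correlations. Unpaired power is Φ[(d√(n/2)/SD − 1.96)/√(1−ρ)], with √20 = 4.472:

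- ρ = 0.3: 3.76 × 4.472/7 = 2.40; (2.40 − 1.96)/0.837 = 0.53; power about 70%
- ρ = 0.5: 3.18 × 4.472/7 = 2.03; (2.03 − 1.96)/0.707 = 0.10; power about 54%
- ρ = 0.7: 2.46 × 4.472/7 = 1.57; (1.57 − 1.96)/0.548 = −0.71; power about 24%

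Simulation gives 69%, 52% and 23%. This is the loss if Student's t-test is run unpaired.

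**3. Power of the fallback on skewed scores.** These are the scores that can reach it. Simulated, same changes, SD and n:

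| Shape | Test | ρ 0.3 | ρ 0.5 | ρ 0.7 |
|---|---|---|---|---|
| Gamma(2) | Mann-Whitney | 82% | 72% | 46% |
| Gamma(2) | Signed-rank | 83% | 85% | 83% |
| Exponential | Mann-Whitney | 94% | 87% | 72% |
| Exponential | Signed-rank | 90% | 87% | 89% |

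Repeat runs differ by a few points (42% to 46% for the gamma(2), ρ = 0.7 Mann-Whitney cell).

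**4. How often the fallback is used.** At n = 40 the critical value is 0.210 for plain K-S and 0.138 with the Lilliefors correction. Before and after scores are each tested.

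- Gamma(2): about 10% of trials with plain K-S, about 82% with Lilliefors. The 10% fits a single-variable rejection rate of about 5%: 1 − 0.95² = 0.0975.
- Normal scores: almost never with plain K-S, about 10% with Lilliefors (again 1 − 0.95²).

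**5. A 7-point change.** 7 × 4.472/7 = 4.472, and Φ(4.472 − 1.96) = Φ(2.51) = 0.994 even at ρ = 0. Paired power is about 1.00. The choice of test does not matter here.

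**6. Response proportions in the same patients.** Pearson chi-squared has simulated true size 3.5%, 2.4% and 0.8% (McNemar 4-5%). With assumed response rates of 35% and 65%, power is 82%, 84% and 85%, against 85%, 90% and 95% for McNemar.

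**The case against.** The strongest reply is that the bad branch is seldom reached. On normal scores Mann-Whitney does fall well below 80% (about 66%, 49% and 22%), but plain K-S almost never sends normal scores there. For the whole rule (plain K-S on raw scores, then paired t or Mann-Whitney), power with gamma(2) scores is 79%, 79% and 74%, against 79%, 80% and 76% for always using paired t. With exponential scores it is 86%, 83% and 77%, against 79%, 77% and 76%. This stands for plain K-S with a paired t-test, but the plan states neither. With a Lilliefors pretest, gamma(1.5) scores and a 2.1-point change, the rule has 41%, 41% and 38%, against 42%, 56% and 73% for signed-rank.

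Four stronger readings are tempting, and the documents do not support them:

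- **Inflated false positives.** Under positive correlation the error runs the other way.
- **Pairing lost throughout.** This is certain only in the fallback, because the t-test is not labelled either way.
- **The pretest itself spoils the error rate.** It does little harm when both branches are valid. The damage comes from the branch it leads to.
- **Chi-squared is wrong as such.** The plan does not say which proportions are compared. For different patients, such as the two sequence groups, Pearson chi-squared and Mann-Whitney are suitable.

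**Conclusion.** The concern holds in limited form. The plan names an independent-samples test for a paired comparison and names no paired test, so the rule is wrong for the design as written. The consequence is conservatism and lost power. In the fallback the loss ranges from none (exponential scores, ρ up to 0.5) to 83% falling to 46% (gamma(2), ρ = 0.7). If the t-test is run unpaired, normal scores suffer too.

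A before/after ISI change of about 1 SD would still be found. What is exposed are smaller changes, the secondary scores and the BBT-I versus zopiclone contrast, which is also within-patient and is the primary objective. There, a missed difference could be read as equivalence.

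These sizes rest on the assumed correlations and score shapes, an SD of 7, and scores not rounded or bounded to the 0-28 scale. The point should be fixed, but it is not critical.

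**What to change.** 1. Delete the normality pretest in both endpoint sections and in the synopsis.
2. For before/after comparisons, state the paired t-test, with the Wilcoxon signed-rank test on within-patient differences as sensitivity analysis. Alternatively, state signed-rank as the single test.
3. Use McNemar's test where response or remission under the two treatments is compared in the same patients.
4. Keep Mann-Whitney and Pearson chi-squared for comparisons of different patients, such as responders versus nonresponders, and say so.
5. For BBT-I versus zopiclone, specify a within-patient crossover analysis with treatment, period and sequence. Do not adjust for the second-course baseline at Visit 3 as if it were untreated. It follows the first course, and Study Overview uses that interval to observe whether the effect lasts, so the adjustment could absorb carryover.

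The cost is a minor change of analysis wording. No patients, visits or measurements are added. If a mixed model is chosen for item 5, the software needs a suitable routine.

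### The plan names ISI change as primary but places response and remission, with a test of proportions, under the same headings, and no rule says which result decides BBT-I versus zopiclone

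*Combined protocol and SAP*

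**What the plan says.** The synopsis gives the primary endpoint only as the ISI, without metric, contrast or time point. The protocol section Primary Efficacy Endpoint is more specific: "Proposed primary efficacy endpoint is change of insomnia severity index (ISI) after treatment". Under the same heading it goes on to define response, remission and nonresponse.

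Analysis of Primary Endpoint contains four elements:

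- A test of the score: "Statistical significance of differences between ISI level before and after treatment for both treatment methods will be evaluated with Student's t-test", with a Mann-Whitney fallback if the distribution is not normal.
- A test of proportions: "For comparison of the proportions Pearson chi-squared test will be performed". The proportions are not named. The same sentence stands in the synopsis statistics and in Analysis of Secondary Endpoints.
- The response definition: "Criterion of response to the treatment is defined as the reduction of ISI score reduction of >7 points from baseline".
- The remission definition: "Remission criterion is defined as final ISI score of 7 points or less".

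The error rate is given once for everything, in the synopsis statistics and in Analysis of Secondary Endpoints: "Statistical significance will be set at a p-value less 0,05". There is no hierarchy, no adjustment, and no statement of which result carries the primary conclusion. The response split has one explicit use, which is to form responder and nonresponder groups for the predictor analysis.

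**The concern.** The primary objective is a comparison of two methods. A reader cannot tell from the plan whether it is settled by mean ISI change, by the response rate, by the remission rate, or by whichever of them is significant. The three are derived from the same score but need not agree, because two of them depend on where patients fall relative to a cut-off.

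The setting makes the gap worth closing. The trial is open-label, there is no data monitoring committee, and the investigator is responsible for processing and reporting the data. If the results differ, nothing written in advance stops the favourable one from being presented as the primary answer. If any of several 5% tests may carry the claim, the chance of a false claim exceeds 5%.

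**Working it through.** **Inputs from the documents.** Sample size: "The number of subjects planned to be enrolled is 40". Design: "every patient will receive two different treatment courses in random sequence", so comparisons between methods are paired. Threshold: p<0.05 (two-sided is assumed, since the plan does not say). Response: drop of more than 7. Remission: ISI of 7 or below. ISI range: 0-28. Pretreatment SD: about 7, because Analysis of Primary Endpoint equates the response cut-off with about one SD. The plan gives no overall error rate and no power calculation, so it has no figure to reproduce beyond the 0.05.

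**Assumptions not in the documents.** Baseline mean 18; baseline SD 4 or 7; mean drop 6-8; SD of change 5; correlation of change between a patient's two courses 0-0.5; both courses measured from one shared baseline; no true difference between methods; and a rule that any one significant result wins.

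**Step 1, bounds.** For k independent tests at 0.05, P(at least one) = 1 − 0.95^k.

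- k = 3: 1 − 0.857 = 14.3%. The upper bound is 3 × 0.05 = 15%.
- k = 2: 1 − 0.9025 = 9.75%.

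**Step 2, effect of correlation.** For three equally correlated two-sided z-tests the rate is 12.5% at r = 0.5, 10.9% at 0.7, 9.8% at 0.8, 8.3% at 0.9 and 7.3% at 0.95. For two tests it is 9.0% at 0.5, 8.3% at 0.7 and 7.0% at 0.9.

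**Step 3, simulated ISI data.** Trials of 40 crossover patients with integer scores, 20,000 per scenario. Each row gives the chance that at least one test has p<0.05.

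| Tests between methods | Correlation 0 | 0.3 | 0.5 |
|---|---|---|---|
| Paired t plus McNemar for response and remission | 10-11% | 11% | 11% |
| Paired t plus McNemar for response only | 8% | 8% | 8% |
| Paired t plus unpaired Pearson chi-squared for both | 9-10% | 7-8% | 6-7% |
| Unpaired t plus unpaired Pearson chi-squared for both | 8-9% | 5% | 2-3% |

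A wider grid for the first row (change SD 4 or 6, mean drop 4-10) gives 10.2-12.8%. At the assumptions above, 10-12% describes it fairly.

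**Step 4, reading the last row.** The decline does not show that the plan controls multiplicity. With positive correlation, an unpaired test on paired data uses too large a standard error. At correlation 0.5 the unpaired t-test alone rejects in under 1% of null trials, where 5% is intended. Restoring the pairing that the crossover design calls for brings back the first row.

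**Step 5, after the change.** One designated test at 0.05 has a 5% error rate for the primary claim. Splitting the threshold instead, 0.05/3 = 0.0167 per test, gives 1 − (1 − 0.0167)^3 = 4.9% if the tests are independent, and less if they are correlated.

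None of these figures includes the interim analysis after 20 patients, which is a separate matter.

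**The case against.** The strongest reply is that the plan does name one primary endpoint, ISI change, and calls response and remission criteria, not endpoints. The chi-squared sentence names no proportion and recurs word for word in the general and secondary statistics, so it may be a stock line. No sentence says that remission is tested between methods, and no sentence says that any one significant result suffices. Moreover, the score test under the primary heading compares before with after for each method, so an error rate for a between-method claim is hard to define until that comparison is specified. Finally, with the unpaired tests named in the plan, a plausible positive correlation leaves little or no inflation.

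Most of this stands. A reader might infer that the plan sets up three co-primary tests and that, as written, it carries a false-positive rate of 7-12%. The documents do not support that: the co-primary status is inferred, the any-one-wins rule is supplied by the reader, and the rate depends on assumed values and on which tests are run.

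Two things do not fall. First, the predictor analysis does not account for the chi-squared sentence under the primary heading: it compares baseline quantitative characteristics by t-test or Mann-Whitney and uses only the response split. Remission has no stated use outside the primary endpoint. Testing these proportions is therefore the natural reading, though not the stated one. Second, the low error rate with unpaired tests is a by-product of ignoring the design and gives no assurance about the choice among results.

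**Conclusion.** The point holds as a gap in the decision rule. ISI change is named as primary, response and remission stand under the same headings beside a test of unnamed proportions, one threshold covers all, and nothing says which result decides the comparison of methods.

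The size is conditional. If response and remission are tested between methods, and any one significant result may carry the claim, correctly paired 5% tests give roughly 10-12% for three measures and about 8% for ISI change plus response. With unpaired tests throughout, it is about 8-9% at correlation 0, about 5% at 0.3 and 2-3% at 0.5. All of these rest on the assumed ISI SD of 4-7, change SD of 5 and correlation of 0-0.5. No figure is offered for how often the three results would disagree. The case for acting rests on the missing rule more than on any one percentage.

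**What to change.** State the following in the synopsis (Primary Endpoint and Statistics), in Primary Efficacy Endpoint and in Analysis of Primary Endpoint, in matching words:

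- The single confirmatory test, at p<0.05, is the BBT-I versus zopiclone difference in continuous ISI change, analysed within patient.
- Response and remission are reported by method with 95% confidence intervals. They are supportive and cannot establish a difference between methods on their own.
- The before-versus-after comparison within each method is descriptive. Where the chi-squared sentence is kept, name the proportions it applies to.

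This gives the stated objective a named between-method test, which the before-versus-after wording of Analysis of Primary Endpoint does not. It needs no extra patients, visits or data. The cost is that no primary claim can rest on response or remission alone, even if one of them turns out to be the clearest difference.
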